8.5 Other Safety Measures

- Tubular extraction rate (TER):

Relative change from baseline by treatment arm and by visit.

Box plot of raw data by visit and by treatment arm.

- Glomerular filtration rate (GFR)

GFR will be calculated based on the CKD-EPI equation (2021):

$$\text{GFR} = 142 * \min(\text{Scr}/\kappa, 1)^{\alpha} * \max(\text{Scr}/\kappa, 1)^{-1.200} * 0.9938^{\text{Age}} * [1.012 \text{ if female}]$$

Scr is serum creatinine in mg/dL, κ is 0.7 for females and 0.9 for males, α is -0.241 for females and -0.302 for males, min indicates the minimum of Scr/ κ or 1, and max indicates the maximum of Scr/ κ or 1.

Relative change from baseline by treatment arm and by visit.

Box plot of raw data by visit and by treatment arm.

- Renal volume (V_{kidney})

Relative change from baseline by treatment arm and by visit.

Box plot of raw data by visit and by treatment arm.

- Frequency of occurrence and severity of abnormal findings in safety investigations:
 - vital signs:

Vital signs include heart rate, temperature, systolic and diastolic blood pressures and weight measurement.

The BMI will be derived from the collected vital signs using the following formula: $\text{BMI} = \text{weight} / \text{height}^2$

In addition to summary table for continuous data (change from baseline), box plots by visits will be generated for all vital signs as well as for variables derived from vital signs (e.g. BMI) by treatment arm.

- 12-lead ECG

ECG parameters will be presented by visit and treatment arm as continuous data (change from baseline) and also classified as follows:

QTc Absolute count

Post-administration value > 500 ms when not present at baseline (new onset)

Post-administration value of > 480 and ≤ 500 ms when not present at baseline (new onset)

Post administration value of > 450 and ≤ 480 ms when not present at baseline (new onset)

Other

QTc Change from baseline:

Change in QTc from baseline of > 30 and ≤ 60 ms

Change in QTc from baseline > 60 ms

Other

PR

ITM-LET-01	Statistical Analysis Plan
-------------------	----------------------------------

PR relative change from baseline of more than 25% increase leading to PR > 200 ms

Other

QRS

QRS relative change from baseline of more than 25% increase leading to QRS > 120 ms

Other

HR

HR relative change from baseline of more than 25% increase leading to HR > 100 bpm

HR relative change from baseline of more than 25% decrease leading to HR < 50 bpm

Other

9 Health related Quality of Life (HRQL)

Health Related Quality of Life (HRQL) will be assessed by EORTC QLQ-C30 and GI.NET21 questionnaires.

Questionnaires scoring including missing data management will be conducted as per EORTC QLQ scoring manuals.

The QLQ C30 and derivatives will be interpreted based on the validated dimensions (15 for the QLQ C30, 9 multi-item scales and 6 single-item measures; 5 multi-item scales for the QLQ GINET21).

For each HRQL dimension, box plots of raw scores by visit and treatment arm will be presented.

Maximum HRQL improvement (total scores relative to baseline) will be summarized by HRQL dimension and treatment arm.

It is also to be noted that the interpretation of an increase or decrease dimension score can have different meaning depending on the nature of the dimension scale itself (e.g. an increase in a positive scale such as global quality of life corresponds to an improvement in the patient status whereas an increase in a negative scale such as symptoms corresponds to a worsening in the patient status).

For QLQ tools the positive scales (increased score represents a improved quality of life or functioning) are global health status and function scales:

- Global health status/QoL
- Physical functioning
- Role functioning
- Emotional functioning
- Cognitive functioning
- Social functioning

Whereas the negative scales (increased score represents a deterioration of symptomatology / problems) are symptom scales, single item domains and all GI-NET domains:

- Fatigue
- Nausea and vomiting
- Pain (SS)
- Dyspnea
- Insomnia
- Appetite loss
- Constipation
- Diarrhoea
- Financial difficulties
- Endocrine scale
- G.I. scale
- Treatment scale
- Social functioning scale
- Disease related worries scale
- Muscle /bone pain symptom
- Sexual function
- Information/communication function
- Body Image

Proportion of patients with stable score or improvement in score of ≥ 10 compared to baseline or deterioration in score of ≥ 10 points compared to baseline score will be tabulated by treatment arm and by visit and overall (best HRQL response) along with the median time to improvement (defined as the time from randomisation until first improvement) and median duration of improvement (defined as the time from first improvement to subsequent deterioration) for the patients with at least 1 HRQL improvement.

Time to HRQL deterioration will be calculated as the time from randomization to the first deterioration for the same domain. Patients with no deterioration are censored at the last adequate HRQL assessment date. Patients with no baseline and/or no follow-up are censored at randomization.

For each domain, a Kaplan-Meier plot will be produced showing time to event by treatment arm and used to generate a point estimate of the median time to event with corresponding 95% confidence interval (CI).

The stratified log-rank test will be used to compare the time to event in the two groups. The hazard ratios (HR) and corresponding 95% CIs will be estimated from a Cox proportional hazards model including randomized treatment as a factor.

For sensitivity analysis purposes, the p-value using a log-rank test not stratified on randomization stratification factors will also be computed as well as the corresponding hazard ratio (Cox model adjusting for the same factors).

Subgroup and/or multivariate Cox model analyses can be performed as deemed appropriate to explore the impact of co-variables on the HRQL results.

10 Dosimetry

Time activity curves of target organs and tumour lesions will be presented.

Descriptive statistics of target organ and tumour lesions absorbed doses in Gy/GBq will be tabulated by cycle (D1 for all patients, D2-4 for sub-study A patients). A summary of the mean absorbed dose and SD (in Gy/GBq and in Gy for 7.5 GBq) will also be presented by target organs and by cycle. The estimated extrapolation of the cumulative absorbed dose to target organs and tumour lesions will be summarised for a theoretical full course 4 doses of 7.5GBq (i.e. 30GBq).

The association between absorbed dose of ^{177}Lu -edotreotide in the tumours and RECIST 1.1 response will be explored, as well as the association between bone marrow absorbed dose and highest CTCAE haematological toxicities (AEs and labs) or kidney absorbed dose and highest CTCAE kidney toxicities (AEs and labs). Association between baseline kidney function impairment and organ dosimetry will also be explored based on baseline eGFR (i.e. classified as <15, [15,30[, [30,45[, [45,60[, [60,90[, ≥ 90 or less categories in case of too low sub-group sample sizes).

Sub-study A and B:

To verify the accuracy of cumulative absorbed dose (AD) estimations to tumours and kidneys from PRRT cycles D1-D4, based on a linear extrapolation of AD measured during D1, full dosimetric imaging will be repeated during subsequent cycles (D2 – D4) in a subgroup of approximately 20 patients (sub-study A).

Quantitative SPECT reconstruction is a recent option to directly derive quantitative information on ^{177}Lu activity distribution in vivo, allowing to assess absorbed doses with supposedly a higher accuracy, compared to planar scintigraphy. In selected study sites, 3D ^{177}Lu -edotreotide SPECT/CT will be performed in addition to planar scintigraphy (2D). Data will be quantitatively reconstructed and analysed in comparison to planar (2D) and hybrid (2D/3D) dosimetry (Sub-study B).

The following Dosimetry information will be summarised (mean and SD, in Gy) for tumour lesion absorbed dose and kidney absorbed dose:

ITM-LET-01	Statistical Analysis Plan
-------------------	----------------------------------

Table 7: Dosimetry information to be summarised for sub-studies A and B

Dosimetry	C1	C2-C4
Planar	Measured (All patients, Sub-A, Sub-B)	Extrapolated vs. measured (Sub-A, Sub-B) (Sub-A)
	Vs.	Vs.
Hybrid	Measured (All patients, Sub-A, Sub-B)	Extrapolated vs. measured (Sub-A, Sub-B) (Sub-A)
	Vs.	
3D	Measured (Sub-B)	Extrapolated (Sub-B)

Sub-study C:

Blood radioactivity will be measured in sub-study C patients at different time points during and after administration. Blood radioactivity (time activity curves) will be used to calculate the bone marrow absorbed dose.

Descriptive statistics of blood derived bone marrow absorbed dose will be tabulated. A summary of the mean absorbed dose and SD (in Gy/GBq, Gy for 7.5 GBq and Gy for 30GBq) will also be presented.

11 Pharmacokinetics

To investigate pharmacokinetics (PK), blood and urine samples will be collected from 20 patients who received their first dose of ¹⁷⁷Lu-edotreotide. Blood and urine radioactivity will be measured. Blood radioactivity will be used to calculate a surrogate bone marrow dose (see Section 0). Urine radioactivity will be used to measure rate of excretion. In addition, urine samples will be analysed for drug metabolites with HPLC. As no comparisons are performed, 20 subjects are considered sufficient for this PK analysis. The following PK variables will be analysed:

- Urine radioactivity in % of injected activity (%IA) at pre-defined intervals within 48 hours post-injection to assess excretion pattern
- Blood radioactivity in %IA at pre-defined time points post-injection to assess clearance pattern
- Radiochemical purity assessed through HPLC of urine samples collected within 48 hours post-injection

12 Other Analyses

Not applicable.

13 Tables, Figures and Listings

Tables, Figures and Listings specifications including mock-ups will be prepared in a separate TFL tracker attached to this SAP.

14 Reporting Conventions

P-values ≥ 0.0001 will be reported to 4 decimal places; p-values less than 0.0001 will be reported as “<0.0001”. The mean, standard deviation, and any other statistics as median or quartiles, will be reported to one decimal place greater than the original data. Minimum and maximum will use the same number of decimal places as the original data. Estimated parameters, not on the same scale as raw observations (e.g. regression coefficients) will be reported to 3 significant digits. Confidence limits will be presented using the same number of decimal places than the centre point of the CI.

Percentages will be rounded off to 1 decimal place. Rounding errors in the sum in table listings will not be aligned to 100%.

15 Technical Details

All statistical evaluations, including graphical data summaries, will be performed using appropriate software (preferably SAS® statistical analysis software (version 9.2 or higher, SAS Institute Inc., Cary, NC, USA or R, R Foundation for Statistical Computing, Vienna, Austria).

16 Supplementary Analyses

In case additional analyses are considered necessary, amendments to the protocol and to the SAP are to be produced describing the needed analysis in detail. Otherwise such additional analysis will be considered “post-hoc” analyses.

17 Open-label Rollover Post-treatment Extension in France

This section provides a description of the strategy and methodology to be used to perform the analysis of the data generated in Appendix 6 of the Study Protocol (Version 8.3) Amendment 11 (France Only): Open-label Rollover Post-treatment Extension to Enable Access to 177Lu-edotreotide PRRT in Patients Treated with Everolimus who Discontinued Due to Tumour Progression.

The open-label rollover post-treatment extension is to enable patients who received everolimus in the main study and who discontinued treatment due to tumour progression, to receive 177Lu-edotreotide PRRT in France. This section only contains the rollover patients, please refer to Appendix 6 of the protocol for more details.

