Due to tubular re-absorption of radiolabelled peptide agents, radiation-induced kidney disease is the main safety concern for PRRT. Both, acute renal toxicity with increased serum creatinine and long-term nephropathy with creatinine clearance loss (CCL) of 5 to more than 10% per year (Bodei et al., 2008) may occur. Nephropathy is reported to be more pronounced in patients with renal risk factors (arterial hypertension, diabetes mellitus), pre-existing renal impairment or those who have received earlier nephrotoxic treatment modalities (chemotherapy, local EFR, prior PRRT) (Bodei et al., 2008).

All patients in the above-mentioned academic study were pre-treated with a nephroprotective amino acid solution, administered IV starting 30 min to and lasting 3 – 4 h after the start of the PRRT infusion, according to current guidelines (Bodei et al., 2013; Zaknun et al., 2013; IAEA 2013). Such regimen has been shown to decrease the renal absorbed radiation dose by 50% without reducing the tumour uptake (Rolleman et al., 2010). Using this regimen, no clinically relevant nephrotoxicity following PRRT with  $^{177}\text{Lu}$ -edotreotide was observed, as evaluated by extended renal function testing (glomerular filtration rate [GFR], creatinine, tubular extraction rate [TER],  $\text{K}^+$  and BUN).

In the context of the planned trial, a similar nephroprotective regimen will be used. In addition, patients with impaired renal function ( $\text{GFR} < 60 \text{ mL/min/1.73 m}^2$ ), or ill-controlled renal risk factors will be excluded from participation. As a further safety measure, absorbed organ doses to the kidneys will in principle be restricted to  $\leq 23 \text{ Gy}$ , as per current guidelines on PRRT (Bodei et al., 2013; Zaknun et al., 2013; IAEA 2013). If the predicted absorbed dose to the kidneys likely exceeds 23 Gy upon administration of the next PRRT cycle, additional measurement of renal function must be performed. In case this pre-therapeutic TER ( $^{99\text{m}}\text{Tc}$ -MAG3 renal scintigraphy) is  $>50\%$  of baseline, dosing can be continued. However, the absorbed dose is not allowed to exceed 29 Gy, as suggested by Konijnenberg et al. (2007).

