## **4.6 End of the Study**

For regulatory purposes, the end of the study is defined as the last visit of the last patient or the last date of follow-up of toxicities, if required (whichever is later).

The end of study for each individual patient is the visit at month 30, unless disease progression, withdrawal from the study, or death occurs earlier.

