#### **5.4.3.2 DMT during Lu-Edotreotide PRRT**

Dose modifying toxicity (DMT) during Lu-edotreotide treatment is defined as any of the following conditions which are ongoing on day 90 following the preceding PRRT cycle (i.e. at the time of the next scheduled PRRT cycle, as established during the respective pre-treatment evaluations):

- Grade 2 CTCAE or above toxicity for platelet count
- Grade 4 CTCAE lymphopenia
- Grade 3 CTCAE or above toxicity for any other haematological parameter
- 40% increase over baseline in serum creatinine
- decrease of over 40% in creatinine clearance from baseline
- any other Grade 4 CTCAE toxicity considered at least possibly related to study drug, regardless of duration, with the exception of liver enzymes (ASAT, ALAT, AP), which will not be used to define DMT.

Patients experiencing DMT from Lu-edotreotide treatment may receive subsequent PRRT cycles, provided that toxicity has subsided below the values defined above by week 16 following the non-tolerated PRRT administration.

With regard to renal DMT, further PRRT cycles may only be administered, if the following additional conditions are met by week 16:

- Serum creatinine level must be classified CTCAE Grade 0,
- Calculated creatinine clearance must have improved to within 20% from baseline (i.e. at least 80% of initial value)
- The GFR is at least  $\geq 50$  ml/min/1.73 m^2. A GFR value below 50 ml/min/1.73 m^2 will preclude further administration of Lu-edotreotide.

In patients with renal DMT, the eGFR (estimated GFR), needs to be confirmed by a non-radioactive plasma clearance method (e.g. 24 h creatine collection in urine), prior to administration of further administration of  $^{177}\text{Lu}$ -edotreotide, in all cases, where the eGFR is  $\geq 50 \text{ mL/min/1.73m}^2$  and  $\leq 60 \text{ mL/min/1.73m}^2$  at 16 weeks. In cases where eGFR is  $>60 \text{ mL/min/1.73m}^2$  at 16 weeks, no confirmation by a non-radioactive plasma clearance method is required.

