### 8.3.8 Renal Scintigraphy (99mTc-MAG3)

Within 28 days prior to randomisation, each subject will undergo 99mTc-MAG3 (99mTc-mercaptoacetyltri-glycine) renal scintigraphy, to assess the baseline tubular extraction rate (TER) of the kidneys and evaluate the kidney functionality from renogram and sequence images. Follow-up 99mTc-MAG3 renal scintigraphy will be performed in 6-monthly intervals in both groups: at month 6, 12, 18, 24, and 30. For the Lu-edotreotide arm, the month 6 99mTc-MAG3 renal scintigraphy has to be performed within 7 days before administration of the cycle D3 dose of study drug. In case an additional 99mTc-MAG3 renal scintigraphy is prescribed to allow dosing up to 29 Gy to the kidney, it also has to be performed before dosing of study drug (see Section 3.1).

The renal scintigraphy will be performed as clinically established, but in accordance with the details defined in the Clinical Imaging Manual (CIM).

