### 8.3.9 Kidney Function and GFR

Kidney function will be monitored assessing

- Quantitative TER (see Section 8.3.8) determined at baseline, and thereafter in 6-monthly intervals

- GFR calculated from serum creatinine, determined at baseline, thereafter in 3-monthly intervals.
- The calculated GFR will be determined centrally for consistency. Body weight, and height, as well as sex and age will be recorded in the CRF.
- Kidney volume (abdominal MRI/CT, baseline, 3-monthly interval).
- GFR will be calculated using the recommended CKD-EPI formula (Levey et al., 2009)

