**9.2.2.3 Safety and Tolerability Parameters**

- a) Measured tubular extraction rate (TER), percentage depart from baseline value
- b) Calculated glomerular filtration rate (GFR), percentage depart from baseline value
- c) Renal volume ( $V_{\text{kidney}}$ ), percentage depart from baseline value
- d) Frequency of occurrence and severity of abnormal findings in safety investigations (vital signs, 12-lead ECG, clinical laboratory, adverse events)

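### The yearly kidney-function loss that the protocol describes is not estimated as a rate: SAP 8.5 summarises GFR and TER only visit by visit, among a shrinking and unequal set of patients

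*SAP*

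**What the plan says.** Protocol 1.3 names two forms of renal harm from PRRT: acute toxicity with raised creatinine, and long-term nephropathy with "creatinine clearance loss (CCL) of 5 to more than 10% per year". The second is a rate.

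Protocol 9.2.2.3 defines the GFR variable as "Calculated glomerular filtration rate (GFR), percentage depart from baseline value", and TER in the same way. For each, SAP 8.5 plans "Relative change from baseline by treatment arm and by visit" and "Box plot of raw data by visit and by treatment arm". It names no slope, annualised figure or longitudinal model. SAP 5.5 imputes nothing in general.

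On timing, Protocol 8.3.9 has "GFR calculated from serum creatinine, determined at baseline, thereafter in 3-monthly intervals". Protocol 8.3.8 repeats TER in "6-monthly intervals in both groups: at month 6, 12, 18, 24, and 30". Protocol 4.6 ends each patient's participation at "the visit at month 30, unless disease progression, withdrawal from the study, or death occurs earlier". The EOS and early-withdrawal visits (Protocol 7.3.10 and 7.3.11) include serum chemistry and renal scintigraphy, so a last value at exit is planned. After EOS, Protocol 7.4.1 collects late renal toxicity by 6-monthly contact for five years but schedules no GFR or TER. SAP 3.1 does not list renal data among what is collected after EOS.

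Three other renal outputs exist. SAP 8.4 tabulates the worst CTCAE creatinine grade. SAP 10 relates kidney absorbed dose to the worst kidney toxicity. SAP 6.6 counts dose-modifying toxicities (DMTs) with reasons; in the PRRT arm these include a "decrease of over 40% in creatinine clearance from baseline" (Protocol 5.4.3.2).

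**The concern.** A table of mean change at each visit describes whoever is present at that visit. It gives no yearly loss, does not use one patient's successive values together, and specifies no contrast of yearly loss between the arms. The later visits, where chronic nephropathy would show, have the fewest patients, and the everolimus arm empties faster because its assumed PFS is shorter.

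Two things are at stake. One is precision: a real difference in yearly loss may not be visible in the month-24 or month-30 rows. The other is selection: if patients with falling kidney function leave earlier, those who remain look better than the cohort that was treated.

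**Working it through.** **1. Check the PFS assumptions that drive the numbers remaining.** The documents give no power figure for a renal analysis, so the figure to reproduce is the one that fixes the PFS medians. SAP 4 gives 180 events, HR 0.6471 (11/17), 2:1 allocation, two-sided 5% and 80% power.

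Power = Φ(|ln HR| × √(D·p·(1−p)) − 1.96), with |ln 0.6471| = 0.4353.
- p = 1/3: 0.4353 × √(180 × 2/9) − 1.96 = 2.753 − 1.96 = 0.793, which gives 78.6%.
- p = 68/180, the SAP's own event split: 0.4353 × √42.3 − 1.96 = 0.87, which gives 80.8%.

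The stated 80% is reproduced, so the medians can be used.

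**2. Patients still on study.** Assume exponential PFS, with exit by progression or death only: share at month t = exp(−ln 2 × t / median).

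| Arm and median PFS | Month 12 | Month 24 | Month 30 |
|---|---|---|---|
| Everolimus, 11 months (of 100) | 47 | 22 | 15 |
| PRRT, 17 months (of 200) | 123 | 75 | 59 |
| PRRT, 22 months (of 200) | 137 | 94 | 78 |
| PRRT, 30 months (of 200) | 152 | 115 | 100 |

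For example, exp(−0.693 × 24/17) = 0.376, times 200 = 75; and exp(−0.693 × 24/11) = 0.220, times 100 = 22. If the plan's 15% dropout is spread exponentially to month 30 (timing assumed), month 30 holds about 13 of 100 on everolimus and 50 to 85 of 200 on PRRT. None of this needs a renal assumption.

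**3. What the protocol's rate implies.** Compounded, 5% per year is 1 − 0.95² = 9.8% at month 24 and 12.0% at month 30. At 10% per year the losses are 19.0% and 23.2%.

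**4. Precision of a single late visit.** The documents give no SDs, so the following are assumptions: loss of 8 versus 3% per year, slope SD 8% per year, within-patient SD 10%.
- Difference at 24 months: 2 × (8 − 3) = 10 points.
- SD of change: √((2 × 8)² + 2 × 10²) = √456 = 21.4.
- SE: 21.4 × √(1/75 + 1/22) = 5.2.
- Power ≈ Φ(10/5.2 − 1.96), or a little under 50%.

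Simulations with these inputs gave about 45 to 50% for the month-24 comparison and about 85% for a random-slope model on 3-monthly values. On the 6-monthly TER schedule they gave about 40% and 80%. The single-visit calculation does not itself depend on the schedule, so 40 to 50% is best read as one range. With slope SD from 5 to 10 and within-patient SD from 8 to 12, month-24 power ran from 35 to 72% and slope-model power from 76 to 100%.

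**5. Selection, as illustration only.** Assume a mean slope of −5% per year (SD 5), log-hazard SD 0.7 and median 17 months. The true month-30 change is −12.5%. The by-visit mean is −12.5% if exit is unrelated to slope, −10.1% at a correlation of 0.3 and −8.5% at 0.5. The documents give no value for that correlation.

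**The case against.** **By-visit reporting is informative.** The month-12 and month-24 changes are the one- and two-year losses among those present, and by-visit displays suit the acute form of toxicity. SAP 6 allows rank tests between groups and confidence intervals where meaningful, and Protocol 9.3.1 makes secondary variables descriptive. All of this stands, and is why those summaries should stay. It does not supply a rate, or a contrast of rates with an interval.

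**Renal crossings are already counted.** A reader might infer that the plan nowhere counts patients who pass its own renal limits. The documents do not support that, because SAP 6.6 counts DMTs with reasons. The gap is narrower: in the PRRT arm a DMT is judged at day 90 after a cycle, when the next is due, so decline after the last cycle is not counted. Everolimus uses different criteria (Protocol 5.4.3.1), so the arms cannot be compared. Likewise, TER at 50% of baseline is a condition for a further cycle under Protocol 5.4.1.1, not a safety endpoint that was left out.

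**The bias is not established.** A reader might infer that by-visit means will badly understate the loss because patients leave once kidney function falls. No passage makes a patient leave at a stated fall in GFR. Protocol 5.4.3.2 keeps patients with unresolved DMT in the study, while Protocol 11.1.2 requires exit for excessive toxicity. These two passages must be reconciled. If exit is unrelated to renal decline, the by-visit mean is unbiased.

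**The power contrast favours the model.** It sets one visit against all visits, with the model given the true variance components. That is fair criticism: the gain in precision is real, but its size depends on the assumptions.

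**Conclusion.** The point holds in this form. SAP 8.5 does not estimate the yearly loss that Protocol 1.3 uses to describe long-term nephropathy, and specifies no between-arm difference in that loss with an interval. The late visits rest on small and unequal groups: about 75 of 200 and 22 of 100 at month 24, assuming exponential PFS with the plan's 17- and 11-month medians. At a PRRT median of 30 months, half of that arm is still gone by month 30.

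The loss of precision is substantial under the assumed renal inputs, with month-24 power of about 40 to 50% against about 80 to 85% for a slope model, but those inputs are not from the documents. Understatement of the loss is possible and its size unknown. No confirmatory result depends on this. It is an inexpensive improvement to the analysis of the protocol's leading safety question.

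**What to change.** In SAP 8.5, on the SAF, add a linear mixed model for log eGFR and another for log TER, with random intercept and slope and a treatment-by-time term. Report the annual percentage change in each arm and the difference with a 95% CI.

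Use only baseline, scheduled pre-dose or visit, EOS and early-withdrawal values. Exclude the 5 h and 24 h post-infusion chemistry (Protocol 7.3.1 and 7.3.3): it exists only in the PRRT arm and follows a 2 L amino-acid infusion. Because a single slope mixes acute and chronic change, add a change point after the last cycle as a sensitivity analysis.

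Tabulate by arm the number and percentage of patients whose creatinine clearance or eGFR falls more than 40% from baseline at any visit to EOS. TER at or below 50% of baseline may be shown descriptively. Keep the by-visit summaries and box plots, with the number of patients at each visit. Reconcile Protocol 5.4.3.2 with 11.1.2 on whether patients stay in the study.

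The cost is SAP wording, one extra model per variable and one table, with no new data. The model assumes roughly linear loss on the log scale. It corrects for selective exit only so far as exit depends on values already recorded.

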18. Serious non-malignant disease (e.g. psychiatric, infectious, autoimmune or metabolic), that may interfere with the objectives of the study or with the safety or compliance of the subject, as judged by the investigator
19. Clinically relevant renal, hepatic, cardiovascular, or haematological organ dysfunction, potentially interfering with the safety of the study treatments, as follows:
- Renal
    - Renal obstruction
  - Hepatic
    - Total bilirubin >1.5 x ULN
    - AST or ALT >2.5 x ULN
    - Alkaline phosphatase >5 x ULN
    - Albumin <3 g/dL, unless prothrombin time is within normal range
  - Cardiovascular
    - New York Heart Association classification III and IV
    - Uncontrolled hypertension
  - Haematopoietic
    - Platelets  $\leq 80 \times 10^9/L$
    - Absolute neutrophil count (ANC)  $< 1 \times 10^9$  cells/L
20. Pregnant (see Section 8.3.6) or breast-feeding women. Female patients of childbearing potential or male patients with female partners of childbearing potential, unless willing to practice full and true sexual abstinence or who are surgically/permanently sterile (bilateral tubal occlusion, hysterectomy, or vasectomy), or female patients whose male partners have medically successful vasectomy (provided the partner is the sole sexual partner of the female patient of childbearing potential), or who are not willing to practice highly effective contraception in combination with a barrier method of contraception (e.g. condom). Contraception methods that are considered highly effective are: oral or non-oral (injected or implanted) non-oestrogen progesterone-based hormonal method; oral, intravaginal, or

transdermal combined oestrogen and progesterone-based hormonal method; and/or intrauterine device (IUD), and/or intrauterine hormone-releasing system (IUS). Sexual abstinence or the contraception methods described above must be followed throughout the entire study period and for 56 days after treatment in the everolimus group and, 66 days in the PRRT group (10 half-lives of  $^{177}\text{Lu}$ ) after the last treatment cycle (see Section 8.3.1.1).

21. Subjects not able to declare meaningful informed consent on their own (e.g. with legal guardian for mental disorders) or any other vulnerable population to that sense (e.g. persons institutionalised, incarcerated etc.)

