5.6 Baseline Definition

Unless stated otherwise:

- for demographic parameters, tumour assessment, QoL, biomarkers and in general all efficacy related variables, baseline is defined as the last non-missing measurement on or prior to randomisation date.
- for lab, vital signs and in general all safety related variables, baseline is defined as the last non-missing measurement prior to first dosing of study treatment.

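### The two lower QTc new-onset classes in SAP 8.5 require no rise from baseline, so a fall from a higher band into a lower one is counted as new-onset prolongation

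*SAP*

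**What the plan says.** SAP 8.5 (Other Safety Measures, 12-lead ECG) states that "ECG parameters will be presented by visit and treatment arm as continuous data (change from baseline) and also classified as follows". For absolute QTc it lists three classes and a residual class for everything else:

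- The lowest class has both a floor and a ceiling: "Post administration value of > 450 and ≤ 480 ms when not present at baseline (new onset"
- The middle class is built in the same way, one step up: "Post-administration value of > 480 and ≤ 500 ms when not present at baseline (new onset"
- The highest class has a floor but no ceiling. It takes values above 500 ms, under the same baseline condition.

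A separate block classifies the change in QTc. It has one class beginning "Change in QTc from baseline of > 30 and ≤ 60 ms", one for changes above 60 ms, and a residual.

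For safety variables, SAP 5.6 says "baseline is defined as the last non-missing measurement prior to first dosing of study treatment".

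The neighbouring ECG rules in SAP 8.5 are built differently. The PR rule, for example, reads "PR relative change from baseline of more than 25% increase leading to PR > 200 ms". The QRS and heart-rate rules likewise state the direction and size of the change.

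Protocol 4.2.2 sets no QTc limit at entry. Its cardiovascular exclusions are "New York Heart Association classification III and IV" and uncontrolled hypertension. SAP 17.7.3.4 applies the Section 8.5 ECG rules to the French rollover extension by cross-reference.

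**The concern.** The condition attached to each class asks only whether the value just described was absent before dosing. For the two lower classes that value is a band with a floor and a ceiling. A patient above the ceiling at baseline was not in the band, so the condition is met, and a later fall into the band satisfies the whole rule. An improvement is then labelled new-onset prolongation.

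Patients with a long baseline QTc can enter because no criterion bars them on that ground. High baseline values also tend to be followed by lower ones through regression to the mean, so such falls are to be expected without any drug effect.

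At stake is the accuracy of one safety display. The frequency and severity of abnormal ECG findings is a named safety variable (Protocol 9.2.2.3, SAP 3.4.3.2) and is shown by visit and arm. Counts in QTc categories are usually small, so a few misclassified improvements are visible in them.

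**Working it through.** **1. The rule applied to every combination.** The plan gives no figure to reproduce here, so the check is logical. I divided QTc into ≤450, >450–480, >480–500 and >500 ms and took one test value from each range (440, 465, 490 and 515 ms). I then applied the rule as written: count if the post-dose value is in the band and the baseline value is not.

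| Baseline (ms) | Post 440 | Post 465 | Post 490 | Post 515 |
|---|---|---|---|---|
| 440 | Other | new >450–480 | new >480–500 | new >500 |
| 465 | Other | Other | new >480–500 | new >500 |
| 490 | Other | **new >450–480** | Other | new >500 |
| 515 | Other | **new >450–480** | **new >480–500** | Other |

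Nine of the 16 cells count as new onset. Six are rises. Three (bold) are falls, of 25, 50 and 25 ms. No fall can enter the class above 500 ms, because that class has no ceiling.

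**2. The rule with a baseline limit added.** If the baseline must also be at or below the lower limit of the class, exactly the three bold cells move to the residual class. All six rises stay where they were, and the other seven cells are unchanged.

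**3. How many patients.** The documents give no QTc mean, SD or visit correlation, so this step rests on assumptions. Let baseline X and post-dose Y at one visit be bivariate normal with the same mean μ and SD σ and correlation r, with no drug effect. All 300 patients are taken to have both ECGs.

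- Patients at risk of being miscounted: P(X > 480) = 1 − Φ((480 − μ)/σ)
- Patients miscounted: P(480 < X ≤ 500, 450 < Y ≤ 480) + P(X > 500, 450 < Y ≤ 500)

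With σ = 25 ms:

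- μ = 425: 1 − Φ(2.2) = 1.39%, or 4.2 of 300. Of these, 56.0% (r = 0.6) to 59.6% (r = 0.8) are miscounted: 4.2 × 0.560 to 0.596 ≈ 2.3 to 2.5 patients.
- μ = 430: 1 − Φ(2.0) = 2.28%, or 6.8 of 300. Of these, 56.7% to 57.6% are miscounted: 6.8 × 0.567 to 0.576 ≈ 3.9 patients.

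The miscounted patients make up 7.7% to 13.1% of everyone placed in a new-onset class.

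**4. Sensitivity.** Over μ = 420–430 and r = 0.6 or 0.8:

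- σ = 20 ms: 0.3 to 1.2 patients of 300 miscounted
- σ = 30 ms: 3.4 to 7.5 patients of 300 miscounted

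Over the whole grid of σ = 20–30 ms, the share of new-onset counts that are really falls runs from about 2% to 19%.

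**The case against.** **The label could be read sensibly.** A programmer might take new onset to mean that prolongation of at least that degree was absent before dosing, and so would not count a fall from 490 to 470 ms. The table specifications sit in a separate tracker (SAP 13) that is not among the documents and might say so. This stands as a reason not to assume that the final table will be wrong. It does not clear the SAP. Neither document defines the condition that way, and the plain referent is the band named in the same line.

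**Other outputs show the direction.** This also stands. The continuous change-from-baseline summary would show the 20 ms fall, and the change classes would put it in their residual. Under Protocol 8.3.7 the investigator also judges each ECG for normality and clinical significance. None of these corrects the categorical count, but they limit the harm.

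**Stronger readings that the documents do not support.**

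- A reader might infer that the wording can also hide severe prolongation, for example by losing a rise from 455 to 510 ms. That would require testing the class above 500 ms against a 450 ms baseline limit, which nothing in SAP 8.5 suggests. As written, 510 ms is counted because a value above 500 ms was absent at baseline, and the 55 ms rise also appears in the >30 to ≤60 ms change class.
- A reader might infer a bias between arms. None is shown. The rule is the same in both arms, treatment is randomised, and with no drug effect the false counts fall in proportion to arm size. SAP 8.5 presents these data by arm and specifies no test of them.
- A reader might take the 4–7 of 300 patients with baseline QTc above 480 ms as the number miscounted. Only a little over half of them are.

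**Conclusion.** The point holds for the two lower classes. Followed as written, SAP 8.5 counts certain falls in QTc as new-onset prolongation. This is a stated rule that gives a wrong count, and the PR, QRS and heart-rate rules beside it show that direction could have been specified.

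The consequence is minor. Under the assumed distribution in the central setting, about 2–4 of 300 patients per visit are affected, spread over both arms, and fewer at later visits as patients leave. Those figures depend wholly on the assumed mean, SD and correlation; the logical error in the three cells does not. The display is descriptive, and no confirmatory test, stopping rule or eligibility decision depends on it. The correction is worth making because it is nearly free and removes an ambiguity that two programmers could resolve differently.

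**What to change.** Keep the three mutually exclusive QTc classes in SAP 8.5 and add one condition: a patient is counted in a class only if baseline QTc was at or below the lower limit of that class (450, 480 or 500 ms). Equivalently, the post-dose band must be higher than the baseline band. All other cases go to the residual class.

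Cumulative thresholds (>450, >480, >500 ms, each compared with the same threshold at baseline) would flag the same patients but tabulate them differently: a rise from 440 to 510 ms would appear in three rows instead of one. If that layout is preferred, the SAP should say so explicitly.

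The cost is one line in the SAP and the matching line in the table specifications, with no new data. The rollover ECG summaries inherit the change through their reference to Section 8.5.
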